Cover Page

Protocol document version date Sept 27, 2021

Document submitted Nov 25, 2023

NCT # NCT06105138

Title: Cannabidiol Effects on Blood Alcohol Level and Intoxication

Statistical Analysis Plan

Prior to hypothesis testing, we will conduct data wrangling and visualizations on the raw data for all outcomes using the R programming language and packages included in tidyverse (Team 2013; Wickham et al. 2019) (e.g., ggplot2 (Wickham 2016)). To examine changes over time in BrAC, alcohol craving, affect, sedation, and stimulation during the descending limb of the BrAC curve (T2 – T8, see Figure 1) and to compare these changes by sex and condition, we will run a series of Multilevel Structural Equation Models (MSEM; (Mehta and Neale 2005) using Mplus 8 (Muthén and Muthén 2017). Due to the research design, where each participant completed each condition (placebo, 30mg CBD and 200mg CBD) and within each condition there were 7 repeated measures of interest, MSEM need to be run with a latent growth curve on the within-level to capture the change over time. Repeated measures of interest were taken at timepoints T2-T8, which represent the descending limb of the BrAC curve. We will focus on the descending limb because evidence suggests that some subjective effects of alcohol may be particularly prominent during the descending limb (Pihl et al. 2003; Brick 2006). In addition, prior medication studies have demonstrated that notable medication effects such as reduction in craving and stimulation are observed in both the descending and ascending limb (Ray and Hutchison 2007), but some unique effects such as increased tension may be specific to the descending limb (Ray et al. 2008). Another advantage of focusing on the descending limb is that changes during this time are expected to be approximately linear (e.g., BrAC decreases linearly (Posey and Mozayani 2007)), which supports a more straightforward interpretation of model results. Note that T2= 90 minutes after the start of the alcohol administration session and T8=4.5 hours after the start of the alcohol administration session.

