In all models, condition will be treated as a within-person variable, and sex will be treated as a between-person variable. To examine whether condition influenced changes over time, we will regress the latent slope parameter defined by the latent growth curve model on a dummy coded within-person condition variable. As there are 3 conditions, each model must be run twice to assess all pairwise

comparisons. First with placebo as the referent group (i.e., comparing placebo to 30mg CBD and placebo to 200mg of CBD) and then again with 30mg CBD as the referent group (i.e., to get the comparison of 30mg CBD to 200mg CBD). To determine if sex moderates the condition → change relationship we will create a random slope of condition predicting the latent slope variable and then regressed that random slope on the between-person binary sex variable. This is referred to as the random coefficient prediction method (Preacher et al. 2010, 2016). We will also use this method to determine if the overall change over time is moderated by sex by regressing the random latent slope parameter on the between-person sex variable. The MSEM approach allows paths that include within-level effects to have random intercepts and allows for the creation of Bayesian credible intervals for assessing significance of effects. Bayesian credible intervals provide a robust test of direct and moderation effects, are computationally efficient, and are amenable to a variety of variable characteristics (e.g., hierarchical–nested and non-normal data; (Gelman et al. 2004; Muthén and Asparouhov 2012).

#1903 - Exploring the Effects of Acute Cannabidiol Administration on Blood Alcohol Level and Intoxication in Adult Human Subjects

Protocol Information

Review Type	Status	Approval Date	Continuing Review Date
Expedited	Superseded	Sep 27, 2021	--
Expiration Date	Initial Approval Date	Initial Review Type	
Aug 18, 2022	Mar 09, 2021	Full Board	

Feedback

Approval Comment

Amendment [v7] has been reviewed and granted approval by expedited review (§46.110(b)(2)) of minor changes on September 27, 2021. This amendment includes updated recruitment flyer CBD Alcohol Flyer 2. The IRB has determined that the risk level remains unchanged and the safeguards for participants is appropriate. The study was assessed as being in accordance with 45 CFR 46.111 of the 2018 Requirements.

RISK: More than Minimal

SPONSOR: CCTSI

Protocol Amendment Form

Amendment

Amendment Instructions

1. Complete this Amendment overview.

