Study Overview. Heavy drinkers (N=40) who do not regularly use cannabis but are not cannabis naïve will be recruited for this pilot study involving 3 half-day visits to our lab at CSU. Interested individuals will be phone screened, and eligible subjects will be scheduled for their first visit. For both visits, subjects will be asked to arrive in the lab at 11:15am and will be asked to have someone drive them to the lab and pick them up at the end of the day if possible. If this is not possible we will call a Lyft for them and cover the cost. At the first visit, they will complete informed consent and a demographics form and several questionnaires on psychological functioning and substance use. Subjects will then consume their CBD (30 mg or 200 mg) or placebo. Alcohol administration (up to .8g/kg) will occur about 25 min after CBD ingestion, and testing procedures will occur every 30 minutes for the next 4 hours. The timeframe of the visit was selected because maximum plasma concentration of this CBD product occurs in the blood after 45 minutes (Williams et al 2021) Also, peak BrAC occurs for the alcohol dose we are administering (up to .8g/kg) approx. 1 hour after alcohol ingestion. The order of study visits (CBD 30 mg vs. CBD 200 mg vs. placebo) will be counterbalanced across participants, such that participants will be randomly assigned to complete each the three visits in different orders. Also note that the research assistants running the study will also be blinded to participant condition (and a non-blinded graduate student will prepare the CBD product for the subjects before the session). The three study visits will occur 1 week apart. There will also be 3 venous blood draws for Blood Cannabinoids at both visits. Blood draws will occur before CBD/placebo ingestion (to verify no CBD use prior to experiment), before alcohol consumption and 60 min post-alcohol ingestion. Blood will be assayed for CBD, THC and THC metabolites using High Performance Liquid Chromatography-Mass Spectrometry.

This procedure is:

Other Procedure

Please explain:

Overview of procedures/activities.

Procedure Description

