- Who receives and can use the information

For example, persons might not want to be seen entering a place that might stigmatize them, such as a pregnancy-counseling center identified as such by signs on the front of the building.

Describe how you will protect subject's privacy.

Participants are recruited either using targeted mailer or online. Initial screening is conducted via phone, and prospective participants are asked at the beginning of the call if they are in a location where they feel comfortable answering questions about substance use. The study will be conducted in a secure space in [name] research lab at CSU.

Confidentiality is about data. Confidentiality pertains to protecting information from disclosure based on an agreement between the participant and the researcher. When an individual shares information in a relationship of trust and expects it to be kept private or will be disclosed only with specific permissions, researchers must uphold this agreement and maintain data appropriately.

Describe how you will maintain the confidentiality of subjects' information.

The PI and study staff will have access to identifying information, which will be stored in locked filing cabinets. Research data will be stored separately, in a password-protected documents on a secure, password-protected server.

Biospecimens

Identify which type(s) of biospecimens will be used as part of this research project:

Blood

Fecal/Urine Samples

Are the specimens known to be diseased or dangerous

No

Will tissues be stored for future research projects?

Yes

Will tissues or associated data be sent out of this institution as part of a research agreement under a Data Use Agreement or Material Transfer Agreement?

No

Do you require approval through the Institutional Biosafety Committee (IBC)?

Yes

IBC Project Approval Request Form (PARF) # or pending
Project 21-012B

IBC Agent Approval Request Form (AARF) # or pending
not required

For more information or support, contact the CSU IBC at: [contact]

Drugs and Devices

Identify which drugs, reagents or chemicals will be used as part of this research:

Drug/Agent Name
CBD 30 mg and 200 mg CBD products will be sourced by Caliper Foods
Identify Criteria
Cannabis/Hemp/CBD

Participant Population

Are you interacting or intervening with participants?

Yes

Provide an estimate of the anticipated participant total.

20

Are you analyzing existing data records or biospecimens?

No

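### The crossover model leaves out visit, so the CBD condition intervals on the slope are wider than necessary if the slope drifts across the three visits

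*Combined protocol and SAP*

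**What the plan says.** The Statistical Analysis Plan gives the model for the main comparison: "we will regress the latent slope parameter defined by the latent growth curve model on a dummy coded within-person condition variable". It then fixes the covariates: "In all models, condition will be treated as a within-person variable, and sex will be treated as a between-person variable". The available SAP text names no visit, period or sequence term. The data are a three-session crossover: "each participant completed each condition (placebo, 30mg CBD and 200mg CBD) and within each condition there were 7 repeated measures of interest".

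The protocol (Procedures, Study Overview) treats visit order as a design factor. It states "The order of study visits (CBD 30 mg vs. CBD 200 mg vs. placebo) will be counterbalanced across participants" and "participants will be randomly assigned to complete each the three visits in different orders", with this spacing: "The three study visits will occur 1 week apart". It does not say how many orders are used, or whether they are allocated in blocks or by simple randomisation.

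The sample size is 40 in the Study Overview. Under Participant Population, the answer to "Provide an estimate of the anticipated participant total" is 20. The documents give no effect size, slope SD, power calculation or estimate of a visit effect.

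**The concern.** Participants go through the same alcohol session and the same rating scales three times. The first visit also carries consent, demographics and baseline questionnaires. If the rate of change over T2–T8 drifts from visit to visit, the stated model has nowhere to put that drift except the residual.

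- **Near-balanced orders.** The condition estimate stays close to unbiased, but its interval is too wide.
- **Simple randomisation.** Chance imbalance also makes the estimate itself more variable.

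In either case a real condition effect is easier to miss in a small pilot, although visit number is already recorded and would recover most of the loss.

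The point is narrow. Condition is tested on the slope, so only a visit effect on the rate of change matters; a shift that is constant through a session goes to the intercept. Such an effect is least expected for BrAC decline and more plausible for self-rated craving, affect, sedation and stimulation.

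**Working it through.** **Inputs.** From the documents: three conditions, one latent slope per person per visit, random or counterbalanced order, N = 40 or 20. Assumed: a linear drift of d per visit in the slope (−d, 0, +d), in within-person SDs of the per-visit slope estimate; 95% two-sided intervals (the SAP gives no level); complete T2–T8 data. There is no power figure in the plan to reproduce.

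**Closed form, balanced orders.** Visit is then orthogonal to condition, and omitting it moves the visit sum of squares into the residual:

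residual variance ratio = 1 + N·2d²/(2N − 2), which is close to 1 + d².

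At N = 40, d = 0.5: 1 + 40·0.5/78 = 1.256, square root 1.121. The approximation √(1 + d²) gives 1.031, 1.118 and 1.414 at d = 0.25, 0.5 and 1. It also follows from the visit gaps between two conditions over the six orders (+2, +1, +1, −1, −1, −2), whose mean square is 12/6 = 2.

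The excess variance is equivalent to about 6–7%, 26% and 103–105% more participants.

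**Power under exact balance.** The estimator's true variance does not rise; only the reported standard error does. Starting from 80% power (1.96 + 0.84 = 2.80), power = Φ(2.80 − 1.96·√(1 + d²)):

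- d = 0.25: Φ(0.78) = 78%
- d = 0.5: Φ(0.61) = 73%
- d = 1: Φ(0.03) = 51%

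**Simulation.** One slope per person-visit, person effects removed, least squares. Standard error without visit dummies divided by that with them:

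| Orders, N | d = 0 | 0.25 | 0.5 | 1 |
|---|---|---|---|---|
| Near-balanced, 40 | 0.999 | 1.031 | 1.121 | 1.422 |
| Near-balanced, 20 | 0.999 | 1.030 | 1.121 | 1.433 |
| Simple, 40 | 0.987 | 1.018 | 1.103 | 1.396 |
| Simple, 20 | 0.974 | 1.002 | 1.087 | 1.382 |

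- **Near-balanced.** Without the term, coverage rises to about 97% at d = 0.5 and 99% at d = 1: the interval is too wide.
- **Simple.** Coverage stays near 95%, but at d = 1 the SD of the estimate is 0.445 without the term against 0.322 with it (N = 20), and 0.316 against 0.225 (N = 40).
- **Break-even, simple.** 0.987·√(1 + d²) = 1 gives d = 0.16 (N = 40); 0.974·√(1 + d²) = 1 gives d = 0.23 (N = 20).

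**Bayesian growth model.** A purpose-written Gibbs sampler was used with latent intercept and slope over seven times, flat priors and an assumed slope reliability of 0.6. Ratios of 95% credible-interval width at d = 0.25, 0.5 and 1 were:

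- near-balanced: 1.03, 1.12, 1.40 (N = 40) and 1.02–1.03, 1.11, 1.37–1.38 (N = 20)
- simple: 1.01, 1.10, 1.37 (N = 40) and 1.00, 1.08, 1.33 (N = 20)

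**Variations.**

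- If condition effects differ between people (assumed SD 1), the factor is √(1 + d²/1.5) = 1.02, 1.08 and 1.29; simulation gave 1.02, 1.08 and 1.30.
- If only visit 1 differs, by s SDs, the centred sum of squares falls from 2d² to 2s²/3. The ratios are 1.01, 1.04 and 1.16 at s = 0.25, 0.5 and 1.
- For sex by condition, a fit to all three visits gives a cost of about 1.3% (N = 40) or 2.7% (N = 20) when there is no visit effect. A cruder calculation from one pair of visits gives about 3% and 6%, and probably overstates it.

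**The case against.** The strongest reply is that this is optional. Order is already handled by design, so there is no average bias and no inflated type I error. All of the harm depends on a d that no document supplies. d is also per visit: at d = 0.5 and 1 the slopes at visits 1 and 3 differ by 1 and 2 within-person SDs, which is a lot for a rate of change. The one visit difference the protocol does describe, the extra content at the first session, matches the visit-1-only pattern, where the loss is only 1%, 4% or 16%. All of this stands as a limit on size.

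A second reply is that the term could lose precision on BrAC, the Aim 1 outcome, if orders were simply randomised and the drift is below the break-even. That is true, but the loss is at most about 1.3% (N = 40) or 2.7% (N = 20). The cost for sex by condition is of the same order. Neither is a good reason to leave the term out of some models and not others.

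Third, the 80% reference overstates what the term recovers under simple randomisation. At d = 0.25, simulated power without and with the term is 77.2% and 78.6% (N = 40), or 74.8% and 75.1% (N = 20). This is right: at that drift almost nothing is gained.

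Finally, the planned Mplus model with random condition slopes was not fitted. The SAP also uses the past tense ("each participant completed each condition (placebo, 30mg CBD and 200mg CBD") and the cover page gives a submission date in November 2023, so the term would probably be added after data collection. Both points stand, and the second affects how the change should be reported.

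**Conclusion.** The point holds as a conditional, minor to moderate matter of precision. The stated analysis ignores a factor that the design controls and the trial already records. If the slope drifts by about half a within-person SD per visit, omission makes the condition standard errors some 9–12% larger. At 0.25 SD the figure is 0–3%, and at 1 SD it is 38–43%. If condition effects vary between people (assumed SD 1), the near-balanced figures fall to 2%, 8% and 30%.

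These sizes rest on the assumed d, a linear drift, complete data, and stand-ins for the Mplus model. They barely depend on whether N is 40 or 20. Neither total is a multiple of six or of three, so orders cannot be exactly equal in number, and the visit term also removes that residual imbalance. No stated result is shown to be wrong.

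**What to change.** Add two dummies (visit 2, visit 3) as within-level predictors of the latent slope in every model. Add them to the latent intercept only if condition levels are also to be compared. Report the condition contrasts from that model. State which orders were used and whether they were allocated in balance or by simple randomisation, and reconcile the totals of 40 and 20. If results have already been seen, label the term as a later addition and show the contrasts with and without it.

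The cost is a sentence in the SAP and a rerun; visit number follows from the assigned order, so no new data are needed. Each growth factor gains two within-level parameters. If visit has no effect, the condition standard error rises about 0.1–0.2% with near-balanced orders, and about 1.3% (N = 40) or 2.7% (N = 20) with simple randomisation. In the Bayesian fit, with dummies on both growth factors, intervals widen by under 1% in the first case and by about 1.5% or 3.3% in the second.

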Attachment Type

Other

Comments

No Attachment

[CITI_RCR_MC.PNG](#)

Legacy eProtocol ID number

If applicable, enter the ID number this study was previously assigned in eProtocol.

20-10303H

General Questionnaire

Application Type

Full Board

Does this study include use of existing data or biospecimens?

No

Does this study include use of student educational records and data?

No

Does this study include the use of human blood, cells, tissues or body fluids?

Yes

Does this study include evaluation of medical equipment or devices?

No

Does this study include evaluation of drugs, biologics, reagents or chemicals?

Yes

Is this study a clinical trial?

No

Does this study include the use of Protected Health Information (PHI)?

No

Is this study a Graduate Level Thesis or Dissertation Project?

No

Is this study another type of class project?

No

Is the project funded?

Yes

Study Participants

Subjects Checklist (Select All that Apply)

Adults

Collaborators

Will Colorado State serve as the Single IRB for other collaborating institutions on this study?

No, Colorado State University is the only participating institution in this study.

Funding

Funding Sources

Funding Type

Other (i.e. State, Local)

KP Proposal Number or OSP Reference

Number

147332

Title of Grant (if different from protocol title)

CCTSI

Period of Funding

Is the study occurring at CSU?

Yes

Prime or Subawardee?

Prime

Funding was secured by:

CSU Office of Sponsored Programs

Please provide your IRB Approval documentation to Sponsored Programs upon receipt.

Summary and Purpose

Proposed Start Date

February 15, 2021

Proposed End Date

February 15, 2022

Provide a brief summary or abstract of the project, using non-technical terms that would be understood by a non-scientific reader. This summary should be no more than 200 words.

Cannabidiol, or CBD, is commonly found in the cannabis plant and has shown promise in treating alcohol use disorders (AUD). Several rodent studies show that CBD decreases alcohol intake. However, only three human studies have ever been conducted on this topic. These studies showed conflicting results regarding the impact of CBD on intoxication and blood-alcohol level. Importantly, existing studies have used synthetic CBD, which is dissimilar from the plant-based CBD products popular in the U.S. Thus, the conclusions that can be drawn from the existing work are limited, and tightly controlled human studies of the effects of plant-based CBD on blood alcohol level, psychomotor intoxication and subjective intoxication following acute alcohol consumption are needed. In this study, we will explore the effects of two doses of plant-based CBD (compared to placebo CBD) on blood alcohol level, motor and balance impairment as craving/desire for alcohol over the course 4 hours after subjects consume a standardized dose of alcohol. We hypothesize that in the CBD condition, blood alcohol level (estimated using a breathalyzer) will be lower, cognitive and motor/balance performance will be better and craving will be lower for all timepoints. These outcomes have implications for understanding the potential of CBD as an AUD treatment.

Describe the purpose for the proposed project.

The purpose of the project is to improve our understanding of how plant-based CBD products may impact alcohol use among individuals who regularly use alcohol. Since alcohol and cannabis co-use is common in the U.S., CBD is commonly found in recreational and medical cannabis products, and animal research suggests that CBD may decrease alcohol intake, it is important to determine whether CBD have applications for reducing drinking in humans. Ultimately, this could have implications regarding the use of CBD as a potential treatment for alcohol use disorders. Primary objectives are to explore how CBD impacts blood alcohol level, as well as cognitive and motor performance during an acute alcohol administration session. Specific Aims are described in detail below: Aim 1. Assess effects of CBD+alcohol vs. placebo+alcohol on breath alcohol level (BrAC). Hypothesis 1. After consuming CBD, subjects will have lower BrAC throughout the 4-hour period compared to when they consume placebo CBD. Aim 2. Assess effects of CBD+alcohol vs. placebo+alcohol on subjective intoxication. Hypothesis 2a. After consuming CBD, subjects will experience decreased alcohol craving across all timepoints post-alcohol consumption compared to when they consume placebo CBD. Hypothesis 2b. Differences in self-reported stimulation and sedation effects will emerge in the CBD condition compared to the placebo condition across all post-alcohol consumption timepoints. We lack sufficient prior evidence to predict the direction of these effects. Aim 3. Assess effects of CBD+alcohol vs. placebo+alcohol on psychomotor intoxication. Hypothesis 3a. CBD will be associated with better performance on an inhibitory control task compared to placebo across all timepoints. Hypothesis 3b. CBD will also be associated with better balance/motor performance at all timepoints after alcohol consumption compared to placebo.

What do the investigators hope to learn from the project?

We hope to gain a better understanding of the impact of CBD on blood alcohol level. We also hope to better understand whether CBD impacts levels of acute alcohol intoxication (specifically as regards craving, subjective effects of alcohol and cognitive and motor impairment). This has implications regarding CBD's potential as a treatment for alcohol use disorder.

Describe how sharing results of this study could influence behavior, practice, theory, future research designs. Specifically, how will study results apply to a larger population than the studied participants?

The results from this research will be disseminated as publications (estimated at least 3-4 papers total spanning all three main study aims) and as symposia/presentations and posters at national and international conferences.

Background**Provide a brief overview of the relevant background. Discuss the present knowledge, appropriate literature and rationale for conducting the research.**

Increases in alcohol consumption, high risk drinking and AUD constitute a public health crisis in the U.S.(Grant et al., 2017). Although decades of preclinical and clinical research have shed light on risk factors associated with the etiology and maintenance of AUD, currently available interventions demonstrate only modest efficacy (Dutra et al., 2008; Jonas et al., 2014). Thus, there is increasing interest in exploring alternative AUD treatments targeting novel biological systems. Notably, the endocannabinoid system (ECS) has emerged in recent years as a potential treatment target for AUD (Sloan et al., 2017). In particular, the non-psychoactive cannabinoid cannabidiol (CBD) has shown preclinical promise in ameliorating numerous clinical symptoms of AUD. Specifically, CBD reduces the reinforcing properties of alcohol and decreases drinking motivation and consumption in mice (Viudez-Martínez, García-Gutiérrez, et al., 2018; Viudez-Martínez, García-Gutiérrez, et al., 2018) and attenuates cue-induced and stress-induced alcohol-seeking, reinstatement, anxiety, and impulsivity in a rat model of AUD (Gonzalez-Cuevas et al., 2018). Although we lack a complete understanding of the mechanism(s) through which CBD may reduce alcohol consumption and/or ameliorate the clinical symptoms of AUD, CBD is known to modulate several neural pathways implicated in AUD. For example, in one rodent study, administration of CBD during ethanol self-administration was associated with decreased expression of the opioid receptor OPRM1 gene, the GPR55 gene, and the CB1 gene (all of which code for proteins associated with AUD and the reward response to alcohol (Mague and Blendy, 2010; Musella et al., 2017; Parsons and Hurd, 2015), and increased expression of the CB2 gene in the nucleus accumbens (NAcc). This study also found that CBD was associated with decreased expression of the tyrosine hydroxylase gene (TH; an enzyme critical for regulation of dopamine synthesis, and which influences dopamine levels after alcohol administration) in the ventral tegmental area (VTA). Given that the dopaminergic signaling from the VTA to the NAcc is responsible for mediating the rewarding effects of alcohol (Koob, 1992; Spanagel and Weiss, 1999), and that increased TH expression is observed in association with acute and chronic alcohol (Lee et al., 2005; Oliva et al., 2008; Ortiz et al., 1995), it is possible that modulation of reward-related genes in the VTA and NAcc could contribute to the efficacy of CBD in decreasing alcohol consumption. In another study, CBD administered with the opioid receptor antagonist naltrexone decreased ethanol consumption and drinking motivation in mice to a greater extent than either CBD or naltrexone alone (Viudez-Martínez et al., 2018a). This study also found that serotonin 1A (5HT1A) receptor expression was reduced in the dorsal raphe nucleus after CBD+naltrexone treatment. The serotonergic pathway projecting from the dorsal raphe to the NAcc is activated during reward-associated tasks in mice (Liu et al., 2014). Given that chronic alcohol exposure is associated with increased 5HT1A receptor sensitivity and increased ethanol drinking in mice (Kelaï et al., 2006), these studies suggest that reduction of 5HT1A receptor expression in the dorsal raphe may be one mechanism through which CBD reduces the rewarding properties of alcohol. In sum, CBD modulates several neural pathways implicated in AUD, and the next logical step is to explore the effects of CBD on alcohol consumption and other AUD phenotypes in heavy drinking human subjects, as is proposed in this study.

Please describe the expertise you have, or have access to, which prepares you to conduct research in this location and/or with this subject population, including specific qualifications (e.g., relevant coursework, background, experience, and training).

P.I. [name] is a clinical psychologist and neuroscientist studying alcohol and cannabis use. She has been working with this population both clinically and in a research capacity for the past 10 years. [name] has a dual PhD in Clinical Psychology and Neuroscience which was awarded in 2018 from CU Boulder. Additionally, she has published over 34 papers on the topic of substance use, and has presented her work and numerous national and international conferences. [name] has been conducting research on substance users along the Front Range Urban Corridor since she began her graduate work at CU Boulder in 2011. As a post-doc at CU Boulder, she was involved in numerous studies with CU Boulder PIs [name] and [name] studying cannabis and alcohol users across the Front Range. She was also involved in a clinical trial of alcohol dependent individuals in the same geographic region, and independently conducted a dissertation project on alcohol and cannabis co-users while at CU Boulder.

Explain your knowledge of local community attitudes and cultural norms and cultural sensitivities necessary to carry out the research. Thus, [name] has many years of experience working with the substance using population across the Front Range.

Procedures

List all research activity procedures in which a participant will be involved, including follow-up procedures. Please provide details.

Procedure Description

Study Overview. Heavy drinkers (N=40) who do not regularly use cannabis but are not cannabis naïve will be recruited for this pilot study involving 3 half-day visits to our lab at CSU. Interested individuals will be phone screened, and eligible subjects will be scheduled for their first visit. For both visits, subjects will be asked to arrive in the lab at 11:15am and will be asked to have someone drive them to the lab and pick them up at the end of the day if possible. If this is not possible we will call a Lyft for them and cover the cost. At the first visit, they will complete informed consent and a demographics form and several questionnaires on psychological functioning and substance use. Subjects will then consume their CBD (30 mg or 200 mg) or placebo. Alcohol administration (up to .8g/kg) will occur about 25 min after CBD ingestion, and testing procedures will occur every 30 minutes for the next 4 hours. The timeframe of the visit was selected because maximum plasma concentration of this CBD product occurs in the blood after 45 minutes (Williams et al 2021) Also, peak BrAC occurs for the alcohol dose we are administering (up to .8g/kg) approx. 1 hour after alcohol ingestion. The order of study visits (CBD 30 mg vs. CBD 200 mg vs. placebo) will be counterbalanced across participants, such that participants will be randomly assigned to complete each the three visits in different orders. Also note that the research assistants running the study will also be blinded to participant condition (and a non-blinded graduate student will prepare the CBD product for the subjects before the session). The three study visits will occur 1 week apart. There will also be 3 venous blood draws for Blood Cannabinoids at both visits. Blood draws will occur before CBD/placebo ingestion (to verify no CBD use prior to experiment), before alcohol consumption and 60 min post-alcohol ingestion. Blood will be assayed for CBD, THC and THC metabolites using High Performance Liquid Chromatography-Mass Spectrometry.

This procedure is:

Other Procedure

Please explain:

Overview of procedures/activities.

Procedure Description

Laboratory Sessions (CBD 30 mg Session, CBD 200 mg Session and Placebo-CBD Session). At each subject's first session, they will arrive at the lab at approximately 11:15am, undergo informed consent procedures with a trained research assistant, undergo urine pregnancy and drug screening and receive a breathalyzer test. We will use the Intoximeter Alcosensor IV Breathalyzer, which is the gold standard for alcohol research studies. Urine drug screening will test for the presence of illicit drugs (besides cannabis). If urine drug or pregnancy tests are positive, participants will be disqualified from participation. If BrAC is above 0.000, participants will be rescheduled. If all tests are negative, participants will complete a brief demographics form and psychological functioning/substance use questionnaires. Next, they do the first blood draw and will then be given either 30 or 200mg CBD dissolved in water or plain water (as the placebo CBD condition). They will then be asked to wait for 25 minutes in our lab. They will be provided with internet access during this time. Participants are allowed to consume water ad libitum throughout the entire day of the study. Immediately before the alcohol administration procedures begin, subjects will again have their blood drawn and will complete measures of balance/motor performance, inhibitory control, alcohol craving, stimulation and sedation. Specifically, the following measures will be administered to measure alcohol craving, stimulation and sedation: The Biphasic Alcohol Effects Scale (BAES) is a self-report rating scale measuring stimulant and sedative effects of alcohol. It has shown good reliability and validity in AUD. The Subjective High Assessment Scale (SHAS) is a standard self-report measure used to assess subjective responses to alcohol. The Alcohol Urge Questionnaire (AUQ) is a well-established measure of alcohol craving and desire to drink that is commonly used in the context of acute alcohol administration. To test balance/motor function we will use a psychomotor battery designed to capture measures of cognitive and motor impairment in divided attention, decision making, reaction time, motor tracking and balance movements following the intake of drugs or alcohol and designed to be administered repeatedly in a single session to assess changes in impairment without being susceptible to practice effects. Finally, to test inhibitory control we will use the The Flanker Inhibitory Control and Attention Task, which requires participants to focus on a stimulus while inhibiting attention to stimuli flanking it. These measures will be administered on an ipad. Next, participants will consume up to .8g/kg of vodka mixed with orange juice, following procedures from previous alcohol and cannabis co-administration studies. The dose will be reduced 8% for females to adjust for expected BrAC differences between males and females. An .8g/kg dose should produce a peak BrAC of no more than .089% approximately 1 hour after alcohol consumption, which should not significantly exceed the BrAC reached by heavy drinkers during a typical heavy drinking period. There will be a third blood draw at this time (approximately 1 hour after the start of the alcohol administration procedure). As in the three prior human studies of alcohol and CBD co-administration, participants will be asked to consume their alcohol within a 20-min. time period. The above procedures (breathalyzer measurement of BrAC, measures of inhibitory control and balance/motor performance, alcohol craving, stimulation and sedation) will be repeated every 30 min. for 4 hours post-alcohol administration. Participants will be required to reach a BrAC of <.03 before going home, which is estimated to take no more than 4 hours post-alcohol administration, given the elimination rate of alcohol from the body. They will also be required to either have someone pick them up from the lab after the study session is over, or if this is not possible our lab will call them a Lyft, and will cover the cost for them. Participants will be offered snacks after testing is complete to facilitate BrAC reduction. The visit will end at approx. 4:00pm. They will also be required to either have someone pick them up from the lab after the study session is over, or if this is not possible our lab will call them a Lyft. CBD Product. Consistent with the Colorado Department of Agriculture (CDA) and CSU regulations, the 30 mg and 200 mg CBD products will be sourced by Caliper Foods (<https://www.caliperfoods.life/>), which is a CDA compliant product containing <.3%THC (thus qualifying as hemp rather than cannabis, which means it is allowed on CSU's campus). Subjects will consume Caliper's 5% CBD concentrate liquid in water on the day of their CBD study appointment, and they will consume plain water with no CBD on the day of their placebo-CBD appointment. Caliper's CBD readily solubilizes into water within seconds and does not impact flavor, consistency, texture or appearance of the water. Thus, participants will not be able to tell whether they are consuming water containing CBD or plain water. Note that individuals who report very high levels of alcohol consumption on the questionnaires, those that report symptoms of severe depression or suicidality, or those that determine that they do need to seek alcohol treatment will be referred to the Psychological Services Center in the CSU Psychology Department (<https://psychology.colostate.edu/psc/>), Aspenridge recovery (<https://www.aspenridgefortcollins.com/>) and

Mountain Crest, which provides inpatient MH services (<https://www.uchealth.org/locations/uchealth-mountain-crest-behavioral-health-center/>). More specifically, if suicidality is revealed during the study session (i.e., if the participant selects a 2 ("I would like to kill myself") or a 3 ("I would kill myself if I have the chance") on BDI item #9), the study procedures will be stopped and the research assistant will call the PI, [name], who has a PhD in Clinical Psychology. [name] will then conduct a risk assessment over the phone. If participants indicate that they have plans, means and intent to harm themselves, and [name] determines that the participant would be a danger to themselves if allowed to leave the session, procedures for hospitalization will be initiated. At this time, [name] (a licensed clinical psychologist in the psychology department) will be called to assist, as a licensed psychologist is needed to sign off on hospitalization procedures. Please note that this is extremely unlikely to happen, given that we will screen individuals out of participating in the study if the report suicidal ideation on the phone screen. However, because we are administering a self-report measure that asks about suicidality, the procedures described above are in place to ensure participant safety.

This procedure is:

Research Activity Involving Participants, Participants Data, or Biospecimens

This procedure is:

Experimental

Where and when will this procedure take place?

Please identify the location of procedures.

Who will conduct this procedure?**Personnel**

[name]

Personnel

[name]

Personnel

[name]

Personnel

[name]

Personnel

[name]

Indicate the frequency and duration of visits/sessions as well as the subject's total time commitment for the study.

Visits will take about 4.5 hours.

Describe how the data will be collected (i.e. in person or online).

In person

Privacy and Confidentiality

Explain how the established data management plan along with consent processes and other elements of the research design address the

following.

Privacy is considered from the perspective of the participant and is a right to be protected. Privacy refers to an individual's interest in controlling others' access to themselves. Based on their privacy interests, participants may want to control:

- The time and place where they give information
- The nature of the information they give
